10.1 Sample Size Determination

A sufficient number of healthy subjects will be screened so that up to 66 subjects are randomized to participate in the study to ensure 60 evaluable subjects complete the entire study. With a sample size of 60 subjects that complete the study, the study will have 90% power to detect a difference in means of 5.0 in %SMHR at 4 hours, assuming a standard deviation of differences of 11.92 (estimated from GSK study Z2560490, which was a study of similar design), using a paired t-test with a 0.05 two-sided significance level.

A sample size of 60 subjects will be large enough to also detect a difference of 7.4 in RER with 80% power.

A sufficient number of healthy adult subjects will be selected from the Oral Health Research Institute’s IRB approved database of previous research studies or from persons expressing interest in participating in research, and screened for participation.

10.2 Statistical Methods and Analytical Plan

Additional details of the proposed statistical analysis will be documented in the statistical analysis plan (SAP), which will be written following finalization of the protocol and prior to study unblinding.

Treatment differences in the study variables will be tested under the null hypothesis:

H0: there is no treatment difference versus the alternate hypothesis

H1: there is a treatment difference.

10.2.1 Demographic and Baseline Characteristics

Descriptive statistics (number of subjects, mean, standard deviation, median, minimum and maximum for continuous variables, and frequency and percentage for categorical variables) will be provided for demographic, ethnicity, baseline characteristics, concomitant medications, medical history and compliance.

 GlaxoSmithKline	Document Name	208-208_166-clinical-protocol.docx		
	Type	Version	Document Identifier	Effective Date
	eldo_controlled	0.0: Effective	090032d580262109	07-Nov-2017 10:31:16
	Reason For Issue	Auto Issue		

Sodium fluoride and potassium nitrate
208166
Clinical Protocol, 08 Aug 2017

10.2.2 Primary Analysis(es)

The primary efficacy variable is %SMHR after 4 hours of remineralization.

Definition of primary variable:

$$\% \text{ SMH recovery} = [(E1-R)/(E1-B)] * 100$$

B = indentation length (µm) of sound enamel at baseline

E1 = indentation length (µm) after first erosive challenge

R = indentation length (µm) after in situ remineralization

Per subject %SMHR will be determined from the %SMHR calculated for each specimen using five indentations measurements per specimen, averaged across the four specimens at 4 hrs. Therefore, a single observation per treatment for each subject will be used in the statistical analyses. If a subject is missing an enamel specimen, the mean will be computed over the available enamel specimens.

The ANOVA model will include fixed factors for study period and treatment, and a random effect for subject. The baseline SMH and first demineralization level will not be included in the model as covariates as the samples will be preselected so that each sample has a measurement of 43 +/-3 µm (at baseline, B) and 120 ± 20 µm (after the first erosive challenge, E1).

The primary comparison of this study is the 1150 ppm fluoride experimental dentifrice versus the fluoride free placebo (0 ppmF) and must be statistically significant to meet the success criteria. The treatment difference and 95% CI will be presented for the primary comparison and all other %SMHR paired comparisons (classed as secondary and exploratory objectives). P-Values for these secondary and exploratory comparisons will only be presented if the primary comparison is statistically significant.

The assumptions underlying the ANOVA will be examined, and if necessary, a suitable transformation or a non-parametric analysis will be performed (eg paired Wilcoxon Sign Rank test).

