5 STUDY TREATMENTS

5.1 Blinding and Allocation to Treatment/Randomization

Blinding

This is a single blind study, with the examiner being blind to the treatment each subject received. Subjects will not be blind to the treatment that they are receiving.

The study statistician and other employees of the Sponsor who may influence study outcomes are blinded to the product allocation of subjects. The examiner will be blinded to the treatment received. To ensure the examiner and specimen analysts remain blinded throughout the study, the examiner and specimen analysts are not permitted in the room whilst product is dispensed. In addition, subjects should be treated in a separate area. The dispensing and laboratory staff will not be involved in any efficacy assessments during the study. Study site staff that perform study consent can only also dispense the study product but can not perform any other study

GlaxoSmithKline Consumer Healthcare Confidential
 Template Version Effective: 22-Jun-2017

 GlaxoSmithKline	Document Name	208-208_166-clinical-protocol.docx		
	Type	Version	Document Identifier	Effective Date
	eldo_controlled	0.0: Effective	090032d580262109	07-Nov-2017 10:31:16
	Reason For Issue	Auto Issue		

Sodium fluoride and potassium nitrate
208166

Clinical Protocol, 08 Aug 2017

activity. Laboratory personnel that carry out the specimen analysis will also be blinded to product allocation and not be involved in any clinical assessment.

Allocation to treatment sequence

Subjects will be assigned to study product sequence in accordance with the randomization schedule generated by a Vendor under the supervision of the Biostatistics Department, GSK CH, prior to the start of the study, using a validated program. Subjects will be randomized in a Williams square design balanced for first period carryover.

Randomization

GSK CH will provide a randomization schedule to the investigator and, in accordance with the randomization numbers, subjects are planned to receive all treatments in a pre-determined order as specified by the randomisation schedule.

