10.2.3 Secondary Analysis(es)

The secondary efficacy variables are:

- i) % Relative Erosion Resistance (RER) after 4 hours intraoral phase.
- ii) Enamel Fluoride Uptake (EFU) 4 hours intraoral phase.

 GlaxoSmithKline	Document Name	208-208_166-clinical-protocol.docx		
	Type	Version	Document Identifier	Effective Date
	eldo_controlled	0.0: Effective	090032d580267d09	07-Nov-2017 10:31:16
	Reason For Issue	Auto Issue		

Sodium fluoride and potassium nitrate
208166
Clinical Protocol, 08 Aug 2017

Definition of secondary variables

% Relative Erosion Resistance = [(E1-E2) / (E1-B)] * 100

- B= Indentation length (µm) of sound enamel at baseline
- E1= Indentation length (µm) after first erosive challenge
- E2= Indentation length (µm) after second erosive challenge

Per subject % RER will be determined for each specimen using five indentations measurements per specimen, averaged across the four specimens at 4 hours. Therefore, a single observation per treatment for each subject will be used in the statistical analyses. If a subject is missing an enamel specimen, the mean will be computed over the available enamel specimens.

Per subject EFU score will be calculated as follows: microdrill samples from each enamel specimen will be pooled and a value for fluoride content per enamel specimen determined. These values will be averaged across the four enamel specimens for each subject and time point to produce the subject-wise mean enamel fluoride uptake.

Analysis of secondary variables

The same ANOVA model and testing procedure outlined for the primary variable will be conducted on the two secondary variables.

The treatment difference and 95% CI will be presented for all of the comparisons however the p-values for these secondary comparisons will only be presented if the primary comparison is statistically significant.

The assumptions underlying the ANOVA will be examined, and if necessary, a suitable transformation or a non-parametric analysis will be performed (eg paired Wilcoxon Sign Rank test).

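### The only rank test named as a fallback for the crossover ANOVA, a plain paired Wilcoxon, ignores period; naming a period-adjusted rank test instead is a free improvement

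*Protocol*

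**What the plan says.** Protocol section 5.1 sets the design: "Subjects will be randomized in a Williams square design balanced for first period carryover". With three treatments and three periods this means six sequences. Section 10.2.2 gives the primary model: "The ANOVA model will include fixed factors for study period and treatment, and a random effect for subject". It then provides for failed assumptions: "a suitable transformation or a non-parametric analysis will be performed (eg paired Wilcoxon Sign Rank test"). Section 10.2.3 carries the model over to %RER and EFU, "The same ANOVA model and testing procedure outlined for the primary variable will be conducted on the two secondary variables", and repeats the same fallback sentence. In neither section does the fallback mention period.

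Section 10.1 states the planning target: "the study will have 90% power to detect a difference in means of 5.0 in %SMHR at 4 hours". It takes 11.92 as the SD of the within-subject differences and bases the calculation on a paired t-test at the two-sided 5% level.

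**The concern.** The protocol treats period as worth adjusting for in the main model, then offers as its example replacement a test that drops it. In a three-period crossover, each subject's test-minus-placebo difference contains the difference between the two periods in which those products were used, and this depends on the sequence. The ANOVA removes that shift. A signed-rank test on the raw differences does not.

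Trial success rests on the one comparison of test product with placebo for %SMHR at 4 hours, and p-values for all other comparisons are shown only if it is significant. If the fallback were used and the periods differed materially, a real effect could be missed that an equally simple period-adjusted rank test would find. A signed-rank p-value also does not by itself supply the treatment difference and 95% CI that section 10.2.2 promises, and the protocol does not say where they would come from.

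**Working it through.** **Inputs.** From section 10.1: difference 5.0, SD of differences 11.92, 60 completers, two-sided 0.05. From section 5.1: six sequences, taken as 10 completers each. Assumptions: a linear period trend with first-to-last range *g* in %SMHR points (the protocol gives no period effect), and 11.92 free of period variation.

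**The plan's own figure.** SE = 11.92/√60 = 1.539, and 5.0/1.539 = 3.249. Normal approximation: Φ(3.249 − 1.960) = 90.1%. The exact paired t-test gives 89.2%. The stated 90% reproduces.

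**Noise added by period.** With a linear trend, the test and placebo periods are adjacent in 4 of 6 sequences (shift ±g/2) and first and last in 2 of 6 (shift ±g). Added variance = (4/6)(g/2)² + (2/6)g² = g²/2. With balanced sequences the shifts cancel in the mean. The true SE therefore stays at 1.539, while the unadjusted test estimates its spread from SD = √(11.92² + g²/2).

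**Hand approximation (mean-based analogue of the unadjusted test).** Effective cut-off c = 1.96 × SD/11.92; type I error = 2Φ(−c); power = Φ(3.249 − c).

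| g | Added variance | SD | c | Type I error | Power |
|---|---|---|---|---|---|
| 0 | 0 | 11.92 | 1.960 | 5.0% | 90.1% |
| 2.5 | 3.1 | 12.05 | 1.981 | 4.8% | 89.8% |
| 5 | 12.5 | 12.43 | 2.044 | 4.1% | 88.6% |
| 10 | 50 | 13.86 | 2.279 | 2.3% | 83.4% |

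**Simulation of the rank tests (normal errors, balanced sequences).**

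| g | Plain Wilcoxon: type I error | Plain Wilcoxon: power | Rank-sum stratified by period pair: power |
|---|---|---|---|
| 0 | 5.0% | 87.6% | 86–87% |
| 2.5 | 4.7% | 87.1% | 86–87% |
| 5 | 4.1% | 86.3% | 86–87% |
| 10 | 2.3% | 79.3% | 86–87% |

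The stratified test's type I error stayed at 4.6–5.4% throughout.

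**Other error shapes at g = 10.**
- t with 3 df: power 89.6% (plain) against 97.0% (stratified); plain type I error 1.6%.
- Lognormal: power 90.9% against 97.9%; plain type I error 0.9%.
- Against a signed-rank test on period-aligned differences, plain power was 78% vs 87% (normal), 83% vs 92% (t, 5 df) and 85% vs 95% (skewed).

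**Other trend shape.** If the whole shift falls between periods 1 and 2, plain Wilcoxon power is 85.1% at g = 5 and 76.4% at g = 10.

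**Imbalance.** Suppose each of the three sequences with the test product after placebo has 12 subjects and each of the other three has 8. The shifts no longer cancel. The mean absolute shift is 2g/3, so the difference is biased by (36 − 24)/60 × 2g/3 = 0.133g, or 1.33 points at g = 10. Simulated type I error was 5.7% at g = 5 and 7.6% at g = 10. With an 11/9 split the test was still conservative (4.7% and 3.6%).

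**Price of adjusting when g = 0.** Plain 87.4% against period-aligned signed-rank 87.5% (normal errors). The stratified rank-sum test gives up about 1 point with normal errors (87.6% vs 86.5%) and less with t, 3 df (96.8% vs 96.3%).

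**The case against.** The strongest reply is that the protocol does not commit to this test. The Wilcoxon is introduced only as an example, a transformation is also allowed, and section 10.2 defers further detail to the SAP. A period-adjusted rank test would be compatible with the wording. This stands, and it is why the point is small. It does not remove the point, since an SAP author who follows the protocol would naturally adopt the one rank test it names.

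The second reply concerns size, and it also stands. A range of 10 points is twice the effect the trial is powered for. Nothing in the protocol suggests such a drift, given preselected specimens, a single supervised use per visit and a washout before each. If 11.92 was itself computed from raw paired differences in a crossover, it may already contain period variation, and the loss would then be overstated.

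Four stronger readings are tempting but unsupported:
- **The plain test always falls below 5% when periods differ.** This needs near-balanced sequences, as the 12/8 example shows.
- **The ANOVA should decide success even when its assumptions fail.** With t (3 df) errors and no period effect, the plain Wilcoxon has 96.8% power against 90.1% for the ANOVA. At a range of 5 the figures are 96.0% and 90.4%.
- **The Wilcoxon wastes incomplete pairs.** The period-adjusted rank tests proposed here also use within-subject differences.
- **Transformation is unusable because %SMHR and %RER can be negative.** The protocol asks only for a suitable transformation, shifted ones exist, and the argument does not reach EFU.

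**Conclusion.** The point holds as a low-severity free improvement. The named example ignores a factor that the main model adjusts for, and a better rank test is available at essentially no cost.

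Under the stated assumptions (60 completers, near-balanced sequences, true difference 5.0, SD 11.92 free of period variation), the power loss against a period-adjusted rank test is under 1 point at a first-to-last range of 2.5, about 1–2 points at 5, and about 7–11 points at 10. At a range of 10 the plain test's type I error is about 1.4–2.4% with normal, heavy-tailed or moderately skewed errors, and it was 0.9% in the lognormal runs. Marked sequence imbalance can push it above 5%.

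The actual period effect is unknown, so the loss may be negligible. The planned ANOVA is unaffected. The figures are for %SMHR; the mechanism is the same for %RER and EFU, but no size was worked out for them.

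**What to change.** In sections 10.2.2 and 10.2.3, replace the example in brackets with a period-adjusted rank test. Either of these would serve:
- a signed-rank test on test-minus-placebo differences after period effects have been removed (period-aligned);
- a rank-sum test on between-period differences, stratified by the pair of periods in which the two products were used.

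State that the treatment difference and 95% CI will then be the matching Hodges-Lehmann estimate and interval, so that the p-value and the interval come from the same analysis. The SAP can carry the detail.

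The cost is one sentence and a few lines of code, with no extra subjects or data. With no period effect, the aligned version loses no measurable power and the stratified version about 1 point at most.

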10.2.3 Secondary Analysis(es)

The secondary efficacy variables are:

- i) % Relative Erosion Resistance (RER) after 4 hours intraoral phase.
- ii) Enamel Fluoride Uptake (EFU) 4 hours intraoral phase.

 GlaxoSmithKline	Document Name	208-208_166-clinical-protocol.docx		
	Type	Version	Document Identifier	Effective Date
	eldo_controlled	0.0: Effective	090032d580267d09	07-Nov-2017 10:31:16
	Reason For Issue	Auto Issue		

Sodium fluoride and potassium nitrate
208166
Clinical Protocol, 08 Aug 2017

Definition of secondary variables

% Relative Erosion Resistance = [(E1-E2) / (E1-B)] * 100

- B= Indentation length (µm) of sound enamel at baseline
- E1= Indentation length (µm) after first erosive challenge
- E2= Indentation length (µm) after second erosive challenge

Per subject % RER will be determined for each specimen using five indentations measurements per specimen, averaged across the four specimens at 4 hours. Therefore, a single observation per treatment for each subject will be used in the statistical analyses. If a subject is missing an enamel specimen, the mean will be computed over the available enamel specimens.

Per subject EFU score will be calculated as follows: microdrill samples from each enamel specimen will be pooled and a value for fluoride content per enamel specimen determined. These values will be averaged across the four enamel specimens for each subject and time point to produce the subject-wise mean enamel fluoride uptake.

Analysis of secondary variables

The same ANOVA model and testing procedure outlined for the primary variable will be conducted on the two secondary variables.

The treatment difference and 95% CI will be presented for all of the comparisons however the p-values for these secondary comparisons will only be presented if the primary comparison is statistically significant.

The assumptions underlying the ANOVA will be examined, and if necessary, a suitable transformation or a non-parametric analysis will be performed (eg paired Wilcoxon Sign Rank test).

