1.2 Background and Rationale

Justification and need to perform the study

The experimental formulation tested in this study is based on the currently marketed Sensodyne Pronamel dentifrice and tested *in vitro* for a superior performance. In order to support the experimental dentifrice market introduction in the US, an *in situ* investigation comparing the experimental dentifrice with a fluoride free placebo dentifrice (primary objective) and with a relevant marketed dentifrice is needed (secondary objective) to investigate the efficacy in enhancing remineralization and preventing demineralization. Therefore, the aim of this study is to investigate the performance of an experimental dentifrice formulation in promoting enamel remineralization and inhibiting post-treatment enamel demineralization in an *in situ* erosion model, in comparison with a fluoride-free placebo and with a marketed competitor dentifrice product.

The *in situ* model to be used in this study has been extensively used to investigate the performance of the currently marketed Sensodyne Pronamel in previously published studies (Barlow et al 2009) and other GSK CH studies (CCI [REDACTED], [REDACTED], GSK-Z3480664, CCI [REDACTED], GSK-Z6961385).

Study and dose rationale

This clinical investigation will use a previously published *in situ* remineralization model (Barlow et al 2009) which consists of placing pre-eroded sterilized bovine enamel specimens intra orally using a palatal appliance and testing the enhancement of remineralization and prevention of demineralization performance of the experimental formulation after 2 and 4 hours post treatment application based on surface micro hardness measurements. Details of enamel and palatal appliance preparations are specified in protocol Section 7.3. The palatal appliances (Figure 1) will be made for each eligible subject, and each will carry two plastic holders containing a total of eight bovine enamel specimens (four in each holder).

GlaxoSmithKline Consumer Healthcare Confidential
 Template Version Effective: 22-Jun-2017

Document Name	208-208_166-clinical-protocol.docx		
Type	Version	Document Identifier	Effective Date
eldo_controlled	0.0: Effective	090032d580262109	07-Nov-2017 10:31:16
Reason For Issue	Auto Issue		

Sodium fluoride and potassium nitrate
208166
Clinical Protocol, 08 Aug 2017

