2 STUDY OBJECTIVES AND ENDPOINTS

Table 2-1 Study Objectives and Endpoints

Objective(s)	Endpoint(s)
Primary	
To investigate the efficacy of an experimental dentifrice containing 1150 ppm fluoride and 5% KNO ₃ to enhance remineralization of enamel relative to a fluoride free placebo dentifrice.	%SMHR after 4 hrs intraoral phase following a single exposure.
Secondary	
Efficacy	
To investigate the efficacy of an experimental dentifrice containing 1150 ppm fluoride and 5% KNO ₃ to inhibit demineralization of enamel relative to a fluoride free placebo dentifrice.	%RER after 4 hrs intraoral phase following a single exposure.
To investigate the efficacy of an experimental dentifrice containing 1150 ppm fluoride and 5% KNO ₃ to promote fluoride uptake in enamel relative to a fluoride free placebo dentifrice.	EFU after 4 hrs intraoral phase following a single exposure.
To investigate the efficacy of an experimental dentifrice containing 1150 ppm fluoride and 5% KNO ₃ to enhance remineralization, to inhibit demineralization and to promote fluoride uptake in enamel relative to a benchmark comparator containing 1100 ppm fluoride (Crest Pro Health).	%SMHR, %RER and EFU after 4 hrs intraoral phase following a single exposure.
Safety	
To evaluate the oral tolerance of an experimental dentifrice containing 1150 ppm fluoride and 5% KNO ₃ following a single brushing event.	Proportion of treatment emergent oral adverse events post 4 hours intraoral exposure.
Exploratory	
To make all paired comparisons of the efficacy of an experimental dentifrice containing 1150 ppm fluoride and 5% KNO ₃ after 2 hours of intraoral exposure to enhance remineralization of enamel, to inhibit demineralization of enamel and to promote fluoride uptake in enamel.	%SMHR, %RER and EFU after 2 hrs intraoral phase following a single exposure.
To characterize the efficacy of the experimental dentifrice containing 1150 ppm fluoride and 5% KNO ₃ ; the fluoride free placebo; and the benchmark comparator containing 1100 ppm (Crest Pro Health) after 2 and 4 hours of intraoral exposure on resistance to acid challenge.	Summary statistic table of ARR after 2 and 4 hrs intraoral phase.

Abbreviations: SMHR: Surface micro hardness recovery, RER: Relative erosion resistance, EFU: Enamel fluoride uptake, ARR: Acid resistance ratio

GlaxoSmithKline Consumer Healthcare Confidential
Template Version Effective: 22-Jun-2017

Document Name	208-208_166-palataprotocol.docx		

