Type	Version	Document Identifier	Effective Date
eldo_controlled	0.0: Effective	090032d580262109	07-Nov-2017 10:31:16
Reason For Issue	Auto Issue		

Sodium fluoride and potassium nitrate
208166
Clinical Protocol, 08 Aug 2017

This study will be considered successful if the experimental dentifrice demonstrates a statistically significant enhancement of remineralization, as measured by %SMHR in comparison with the placebo dentifrice after 4 hours intraoral phase.

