3 STUDY DESIGN AND SUBJECT POPULATION

This will be a randomized, controlled, single center, single- blind (to the dental examiner and specimen analysts), 3 period, 3 treatment, cross-over, *in situ* design which consists of placing pre-eroded bovine enamel specimens intra orally using a palatal appliance and testing the remineralizing performance of the experimental, comparator and placebo dentifrices 2 and 4 hours post treatment application, based on surface micro hardness measurements. This study will be carried out in healthy adults with a maxillary dental arch suitable for the retention of the palatal appliance. A sufficient number of healthy subjects will be screened so that up to 66 subjects are randomized to participate in the study to ensure 60 evaluable subjects complete the entire study. Subjects will be recruited from an existing panel of subjects pre-fitted with a palatal appliance (IRB approved panel CCI [REDACTED]). For a subject whose appliance does not fit adequately and for whom adjustment of the appliance is not sufficient to obtain proper fit, the subject may have a new appliance made. Surface microhardness (SMH) measures changes in the mineral content of enamel, and is used to calculate surface micro hardness recovery (%SMHR), relative erosion resistance (%RER) and acid resistance ratio (ARR). Fluoride uptake of the experimental dentifrice will be assessed by enamel fluoride uptake (EFU) measurements. For each treatment and subject these measurements will be performed on the same enamel specimen, in the four replicates for each time point. The erosive acid challenge, with a commercially available grapefruit juice, will be carried out *ex vivo* and therefore does not pose a risk to the subject's teeth. The overall study design sequence of events is sketched in Figure 2.

For the aim of this study, a fluoride-free placebo dentifrice will be used as comparator to establish if the fluoride present in the experimental dentifrice can provide and enhancement of remineralization and prevention of demineralization in this *in situ* model. Additionally, a relevant commercially available dentifrice containing 1100 ppm fluoride (as stannous fluoride, SnF₂) will be used as a comparator (secondary objectives) to investigate the superior performance of the experimental dentifrice in enhancing remineralization and preventing demineralization.

	Document Name	208-208_166-clinical-protocol.docx		
	Type	Version	Document Identifier	Effective Date

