10.2.5 Other Analysis(es)

Exploratory efficacy variables are:

- %SMHR after 2 hours intraoral phase
- % RER after 2 hours intraoral phase.
- EFU after 2 hours intraoral phase.
- ARR after 2 and 4 hours intraoral phase

Definition of exploratory variables

%SMHR as defined above per primary variable, and %RER and EFU as defined above per secondary variables.

GlaxoSmithKline Consumer Healthcare Confidential
Template Version Effective: 22-Jun-2017

 GlaxoSmithKline	Document Name	208-208_166-protocol-clinical.pdf		
	Type	Version	Document Identifier	Effective Date
	eldo_controlled	0.0: EFFICACY CURRENT	090032d580267d09	07-Nov-2017 10:31:16
	Reason For Issue	Auto Issue		

Sodium fluoride and potassium nitrate
 208166
 Clinical Protocol, 08 Aug 2017

The ARR will be calculated as follows:

$$ARR = 1 - [(E2-R) / (E1-B)]$$

B= Indentation length (µm) of sound enamel at baseline

R= Indentation length (µm) after in situ remineralization

E1= Indentation length (µm) after first erosive challenge

E2= Indentation length (µm) after second erosive challenge

Analysis of exploratory variables

For %SMHR, %RER and EFU variables the same ANOVA model and testing procedure outlined for the primary and secondary variables will be conducted on these exploratory variables. All pair-wise treatment comparisons will be estimated from the respective models for the variables. The treatment difference and 95% CI will be presented for all of the comparisons made however the p-values for these exploratory comparisons will only be presented if the primary comparison is statistically significant.

For ARR, summary statistic table by treatment and time point will be provided.

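### Do the secondary tests need a fixed order behind the gate on the primary comparison?

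*Protocol*

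**What the plan says.** The primary comparison is experimental dentifrice versus fluoride-free placebo on %SMHR at 4 hours. Protocol section 2 ties success to that comparison alone: "This study will be considered successful if the experimental dentifrice demonstrates a statistically significant enhancement of remineralization", against placebo at 4 hours.

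The other comparisons sit behind it. Section 10.2.2 states for %SMHR: "P-Values for these secondary and exploratory comparisons will only be presented if the primary comparison is statistically significant". Section 10.2.3 states for %RER and EFU: "The same ANOVA model and testing procedure outlined for the primary variable will be conducted on the two secondary variables", and "the p-values for these secondary comparisons will only be presented if the primary comparison is statistically significant". Section 10.2.5 gives the 2-hour endpoints the same gate: "the p-values for these exploratory comparisons will only be presented if the primary comparison is statistically significant". Differences and 95% confidence intervals are shown whether or not the gate opens.

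Table 2-1 lists five secondary efficacy comparisons at 4 hours: %RER and EFU against placebo, and three against the marketed comparator, with endpoints "SMHR, %RER and EFU after 4 hrs intraoral phase following a single exposure". Section 3 describes the purpose of the comparator arm as "to investigate the superior performance of the experimental dentifrice in enhancing remineralization and preventing demineralization". Section 1.2 says a comparison "with a relevant marketed dentifrice is needed (secondary objective) to investigate the efficacy in enhancing remineralization and preventing demineralization".

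Section 10.2 defers further analysis detail to an SAP, to be written after the protocol is final and before unblinding. That plan is not at hand.

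**The concern.** A gate on the primary looks like multiplicity control, but it controls little in the scenario that matters most for the comparator. If the fluoride product truly beats a fluoride-free placebo, the gate will usually open. Three comparator tests then follow with no order and no alpha split. Each appears to be read at two-sided 0.05, a level inferred from the 95% intervals and the reuse of the primary testing procedure.

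Section 3 speaks of superior performance, and section 1.2 links the study to a US market introduction. A reader may fear that one favourable result of three would be reported as superiority over the marketed product, at two to three times the error rate of a single test.

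**Working it through.** **Inputs.** Section 10.1: 60 completers, %SMHR difference 5.0, SD of differences 11.92, two-sided 0.05, 90% power; %RER difference 7.4 at 80% power. Table 2-1: three comparator endpoints. The correlation between endpoints is not given; 0 to 0.7 is assumed, with 0.9 as a further check.

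**Step 1: the plan's own figure.** The standard error is 11.92/√60 = 1.539, and 5.0/1.539 = 3.25. Normal power is Φ(3.25 − 1.96) = 90.1%; the noncentral t with 59 df gives 89.2%. The stated 90% reproduces. At the planned placebo effect the gate therefore opens about nine times in ten.

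**Step 2: any false favourable comparator result, product equal to comparator, gate taken as open.** For independent tests, 1 − 0.975³ = 7.3% (either direction: 1 − 0.95³ = 14.3%). Simulation with correlated endpoints gives:

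| Endpoint correlation | Any of three, favourable |
|---|---|
| 0 | 7.3% |
| 0.3 | 6.8% |
| 0.5 | 6.3% |
| 0.7 | 5.5% |
| 0.9 | 4.2% |

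**Step 3: gate included.** In a simulated 60-subject, three-treatment crossover with a placebo difference of 5.0, the gate opened in about 90% of runs. The gate opened together with a false favourable comparator result in 6.7% of runs at correlation 0 and 5.3% at 0.7. With no placebo effect either, that joint rate was about 0.7%.

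**Step 4: which endpoints carry superiority wording.** Section 3 names remineralization and demineralization, that is %SMHR and %RER, but not fluoride uptake. For two independent tests, 1 − 0.975² = 4.9%; simulation gives 4.2% at correlation 0.7 and 3.5% at 0.9. Zero correlation is hard to defend for this pair. The endpoints come from the same specimens and share E1 and the denominator E1 − B: from the formulas in sections 10.2.2 and 10.2.3, %RER = %SMHR − 100(E2 − R)/(E1 − B).

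**Step 5: which decision rule these rates belong to.**
- *Study success.* This depends on one test. The secondaries cannot change its error rate.
- *Endpoint-specific statements.* Table 2-1 names three separate effects against the comparator, each with its own endpoint. A false favourable statement on any one of them has a 2.5% chance, as a single test should.
- *Superiority if any one of three is favourable.* The rates in steps 2 and 3 apply only to this rule, and it is nowhere in the protocol. Sections 10.2.2, 10.2.3 and 10.2.5 govern when p-values are shown, not what a significant one establishes.

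**Step 6: what an order would cost.** Take the sequence %RER then EFU against placebo, followed by the three comparator tests. It would hold any false superiority to at most 2.5% (simulated 1.6% to 2.4%). Both placebo tests must succeed before a comparator test is reached. With 80% power for %RER (stated) and for EFU (assumed; the protocol gives none), independent endpoints and a significant primary, the chance of stopping first is 1 − 0.80 × 0.80 = 36%. In simulation it is 31%, 27% and 23% at correlations 0.3, 0.5 and 0.7. Counting failure of the primary too, it is 1 − 0.90 × 0.64 = 42% at correlation 0 and 30% at 0.7.

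**The case for a change.** The strongest case for the concern is that the protocol fixes a testing rule of its own, repeats it in three sections, and stops short of saying what happens behind the gate. Deferring detail to an SAP does not change what is written. The comparator comparisons are named objectives with a superiority aim and a commercial purpose, so they are more than descriptive. Even at an endpoint correlation of 0.9 the any-of-three rate is 4.2%, above 2.5%, so the direction does not depend on the assumed correlation.

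The numerical part stands: the gate gives almost no protection when the product beats placebo but equals the comparator. If the sponsor later announced general superiority over the marketed dentifrice from a single favourable endpoint, the any-of-three rate would be the relevant one. That would be a fault in such a claim, not in a plan that does not make it.

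The complaint that exploratory p-values cannot be told apart from the others does not stand. Table 2-1 and section 10.2.5 label the 2-hour endpoints exploratory, and ARR receives summary statistics only.

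**Conclusion.** This is not an error in the protocol. No stated figure, rule or property is wrong: the only success criterion rests on a single test, no familywise control over the secondaries is promised, and each endpoint-specific comparator test keeps its 2.5% directional error. The 7.3% to 5.5% range is correct for three tests, assuming an open gate, no true comparator difference and endpoint correlations of 0 to 0.7. It measures a claim rule that the document does not contain. For the two endpoints to which section 3 attaches superiority wording, the figure is 4.9% to 4.2%.

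Whether to control familywise error across secondaries when success rests on the primary alone is a choice on which reasonable statisticians differ. An order has a real price for the comparator objective, as step 6 shows. An order or a nominal label behind a stated gate also belongs to the detail that section 10.2 leaves to the SAP before unblinding, so its absence here is not a finding.
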